5.1. Number of Groups/Arms		2 arms, 15 participants per arm 30 screened and enrolled (n=24 completers)	Group name(s)	exercise plus placebo (EX+PLA) vs. exercise plus BCAA (EX+BCAA)								

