5.2. Overall Design Select all applicable												
	Randomization				Cluster Randomized							
	Group-Sequential				Adaptive Design							
	Parallel Design				Placebo-Controlled							
	Superiority				Equivalence				Non-inferiority			
Device		Pilot			Pivotal				Post-Approval			
Drug/Biologic		Phase 1		Phase 1/2		Phase 2		Phase 2/3		Phase 3		Phase 4
	Dose escalation		If yes, details →									
	Dose ranging		If yes, details →									
	Sub-studies		If yes, details →									
5.3. Other Design Details: Experimental Test by Phase: The experimental design of this study involves 5 phases, completed over 3-4 months. Phase 1 involves recruitment, screening, and enrollment. Phase 2 involves baseline testing. Volunteers then will be randomly assigned to exercise plus placebo (EX+PLA) vs. exercise plus BCAA (EX+BCAA) (Phase 3). Randomization will be 1:1 using a random number generator, assigning participants down the list in order of eligibility. Phase 4 consists of eight weeks of either 3x/week EX+PLA or EX+BCAA. After the intervention, subjects will undergo final research testing (Phase 5). All research testing and training will occur at the Barshop Institute. Intervention staff and participants will be blinded (double blinded) to supplement allocation. Participants will receive either a supplement or a placebo, both in powder form. Only study team member without direct participant interaction (i.e., statistician) will know supplement allocation. Refer to section 10.1 for further information on randomization and blinding.												

6. Study Population									

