6.1. Study Population(s) Label/Name To add more populations – select a row, copy & paste			6.2. Identify the criteria for inclusion The criteria that every potential participant must satisfy, to qualify for study entry.				6.3. Identify the criteria for exclusion The characteristics that make an individual ineligible for study participation.		
			All individuals in this study population must meet all of the inclusion criteria in order to be eligible to participate in the study				All individuals in this study population meeting any of the exclusion criteria at baseline will be excluded from study participation.		
30 screen and enrolled (n=24 completers); 15/group; Community-dwelling older adults, age 60-80 years of age, with subjective reporting of fatigue (reporting ≥3 on a 1-10 fatigue scale)			
 1) fatigue (participants reporting ≥3 on a 1-10 scale) 2) 60-80 years of age 3) lack of menses for at least one year for women 4) BMI 20-50 kg/m² 5) untrained with regard to structured exercise training (is not currently training more than 2x/week) 				
 1) taking an anticoagulant medication that is unable to be discontinued before biopsies 2) allergic to lidocaine 3) neurologic, musculoskeletal, or other condition that limits subject's ability to complete study physical assessments or training 4) hepatic (LFTs >2.5xWNL), renal (eGFR<45), , and uncontrolled psychiatric disease 5) cognitive impairment (MoCA<21) 		

		6) consuming uncommon supplements (multivitamin, calcium, vitamin D, etc are okay)
		7) uncontrolled depression (CESD \geq 16)
		8) any disease or condition considered to be exclusionary based on the clinical opinion and discretion of the PI
6.4. Will screen failures be allowed to re-screen at a later date?	 No  Yes	If yes, describe criteria below ↓ If participants are able to address criteria for exclusion (e.g., stop taking uncommon dietary supplements), they can be considered for rescreening at a later date.

7. Study Intervention(s) being tested or evaluated

This can include prevention, diagnostic or therapeutic interventions (e.g., drug or device) or educational, health services or basic science interventions (e.g., educational program, health care delivery model, or examining basic physiology)

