Exercise: The 3x/wk for eight weeks exercise protocol is designed to provide a high-volume, moderate-intensity whole body training stimulus for all participants. The sessions will occur at the Barshop Institute and be led by an exercise physiologist.

Aerobic exercise training will start conservatively with a goal of 30 minutes total duration at 40-50% maximal heart rate reserve (HRR) determined according to the formula of Karvonen: Training HR = % (HRmax - HRrest) + HRrest. HRmax is defined as peak heart rate based during a peak Cardiopulmonary Exercise Test (described above). Treadmill exercise is advanced weekly, as tolerated to an intensity of 75-85% HRR for 30 minutes. Additionally, participants will perform resistance exercise consisting of 15 repetitions for two sets and to exhaustion on the third set for five major muscle groups: chest press, knee extension, leg curl, row, and bicep curl. Resistance is gradually increased to account for strength gains when participants are able to complete 20 repetitions on the third set.

BCAA or Placebo: Participants will be randomized 1:1 to eight weeks of BCAA or maltodextrin (PLA) supplementation. Participants will be instructed to consume either ~7-10 g of BCAAs (100 mg/kg body weight) (2:1:1 leucine:isoleucine:valine) or PLA powder. In the Barshop Institute pharmacy, intervention blinded study staff wearing hair net, gloves and a facemask will weigh the required participant dose via nutrition food scale and place the daily dose in disposable condiment containers and labeled with dates for daily intake. Powders will be distributed in a double-blind fashion, identical in color, and dissolved in water or a non-calorie drink of their choice (i.e., Crystal Light). On non-exercise days, participants will be instructed to take the supplement between 9 - 10 am each morning and to log each intake in a provided spreadsheet. Powders to be consumed on non-exercise days will be pre-packaged containers and provided to participants on a weekly basis. On exercise days, the supplement will be consumed immediately after finishing exercise training. Supplement containers also will be returned every two weeks to track compliance. Assessment of side effects will occur at every exercise session.

Post Intervention Testing (Phase 5): Participants will repeat tests outlined in Phase 2 and the submaximal exercise test outlined in Phase 3.

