	N/A - An Investigator Brochure is attached
	N/A - A Drug/Device Manual is attached
9.1. Acquisition and accountability State how the study intervention and control product will be provided to the investigator. Describe plans about how and by whom the study intervention will be distributed, including participation of a drug repository or pharmacy, and plans for disposal of expired or return of unused product.	

This study will utilize over-the-counter dietary supplement powders, neither of which require regulation by the FDA. Each will be purchased online and shipped to the Barshop Institute and stored in the clinical pharmacy.
 
The BCAA supplement we will utilize is manufactured and distributed by Naked Nutrition. 1 scoop (1Tbsp) contains 2500 mg of L-leucine, 1250 mg of L-isoleucine, and 1250 mg of L-valine and sunflower lecithin.
 
The maltodextrin placebo we will utilize is manufactured and distributed by nutricost. 1 scoop (15 g) contains 14 g of carbohydrate (maltodextrin).
 
Study staff will distribute the supplement to participants weekly and will ask for unused containers to be returned weekly. The distribution of supplement will be logged by study staff. Participants also will keep a log of supplement intake.
 
Expired and returned product will be discarded following pharmacy protocol.
	
9.2. Formulation, Appearance, Packaging, and Labeling Describe the formulation, appearance, packaging, and labeling of the study intervention and control product, as supplied. Information in this section can usually be obtained from the IB or the package insert, or device labeling. This section should include the name of the manufacturer of the study intervention and control product.	

Intervention blinded study staff wearing hair net, gloves and a facemask will weigh the required participant dose via nutrition food scale and place the daily dose in disposable polypropylene condiment containers and labeled with dates for daily intake.
	
9.3. Product Storage and Stability Describe storage and stability requirements (e.g., protection from light, temperature, humidity) for the study intervention and control product. For studies in which multi-dose vials are utilized, provide additional information regarding stability and expiration time after initial use (e.g., the seal is broken).	

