
The supplement will be stored per distributor recommendations (cool, dry place) in the Barshop clinical pharmacy.
	
9.4. Preparation Describe the preparation of the study intervention and control product, including any preparation required by study staff and/or study participants. Include thawing, diluting, mixing, and reconstitution/preparation instructions in this section. For devices, include any relevant assembly or use instructions.	

On exercise days, both powders will be dissolved in ~400 ml of a non-caloric drink of their choice (i.e., Crystal Light) in the clinical pharmacy by study staff. On non-exercise days, participants will be provided with the Crystal Light and provided written instruction to prepare the mixture.
	

10. Study Intervention Additional Details	
10.1. Measures to Minimize Bias: Randomization and Blinding This section should contain a description of randomization and blinding procedures (if applicable to the study design). It should include a description or a table that describes how study participants will be assigned to study groups, without being so specific that blinding or randomization might be compromised. Plans for the maintenance of trial randomization codes and appropriate blinding for the study should be discussed. The timing and procedures for planned and unplanned breaking of randomization codes should be included. Include a statement regarding when unblinding may occur and who may unblind. Provide the criteria for breaking the study blind or participant code. Discuss the circumstances in which the blind would be broken for an individual or for all participants (e.g., for serious adverse events (SAEs)). Indicate to whom the intentional and unintentional breaking of the blind should be reported.	

Randomization codes will be created at random and kept electronically by a study team member not directly involved with participants (i.e., statistician). We anticipate that blinding will only be broken prior to completion of the study if requested by the DSMB due to safety concerns. Unblinding prior to study completion will be reported to the IRB, study sponsor and DSMB.
 
Randomization code: a random number generator will be used utilizing numbers 1 and 2 where 1=placebo group 2= BCCA group
	

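### The plan states no restriction on the allocation list, so 15 per arm is not secured (small power cost), and the supplied text does not say how blinded weighers of two branded powders stay blinded

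*Combined protocol and SAP*

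**What the plan says.** **Allocation.** Section 5.1 plans "2 arms, 15 participants per arm", and section 6.1 repeats the target: "30 screen and enrolled (n=24 completers); 15/group". Section 5.3 gives the method: "Randomization will be 1:1 using a random number generator, assigning participants down the list in order of eligibility". Section 10.1 adds the code: "a random number generator will be used utilizing numbers 1 and 2 where 1=placebo group 2= BCCA group". The supplied text mentions no blocks, no fixed number of each code, no stratification and no limit per arm. Section 10.1 has the codes kept electronically by a team member not directly involved with participants.

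**Dose preparation.** Section 5.3 limits knowledge of the arms: "Only study team member without direct participant interaction (i.e., statistician) will know supplement allocation". Sections 7 (BCAA or Placebo) and 9.2 give the weighing to staff described as blinded to the intervention, who "will weigh the required participant dose via nutrition food scale". Section 7 sets the BCAA dose by body weight, so preparation is individual. On the stock, section 9.1 says: "The BCAA supplement we will utilize is manufactured and distributed by Naked Nutrition". The maltodextrin is a retail product from a different manufacturer. The masking details given are that the powders match in colour and are handed out double-blind (section 7), and that containers carry dates (section 9.2). Section 9 also ticks "N/A - A Drug/Device Manual is attached" and, likewise, an investigator brochure. Neither was among the documents supplied.

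**The concern.** A generator that returns 1 or 2 independently for each participant gives 1:1 only in expectation. With 30 people the arms will usually differ in size, whereas sections 5.1 and 6.1 state 15 in each. At stake are some loss of precision and a planned arm size that the described method does not deliver.

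The second gap concerns the double-blind claim. Someone has to take each participant's powder from one product or the other. If the two products stand in the pharmacy in their retail packaging, a person weighing from them can see which is which, yet section 5.3 allows only the statistician-type member to know. Fatigue is a named primary outcome (section 12.4). It is measured partly by questionnaires and effort-dependent tests (section 8.6), which are more open to influence by staff who know the arm than the tryptophan assays are.

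**Working it through.** **Inputs.** 30 enrolled, 15 per arm, 24 completers (sections 5.1, 6.1, 12.2). Between-group effect 0.25 and SD 0.25 µmol/L (12.2), so d = 0.25/0.25 = 1. Independent-sample t-test on change, two-sided, 5% level (12.2, 12.4).

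**1. The plan's own figures.** The dropout step reproduces: 24/(1 − 0.20) = 30. The power statement does not. At 12 per group the non-centrality is 1/√(1/12 + 1/12) = 2.449 on 22 degrees of freedom, and two-sided power is 64.9% (68.8% by normal approximation), not at least 80%. That shortfall is a separate matter. Here 64.9% serves only as the baseline, so that the effect of the allocation method stands alone.

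**2. Chance of the planned split if allocation is simple.**
- P(15:15) = C(30,15)/2³⁰ = 155,117,520/1,073,741,824 = 0.1445.
- P(11:19 or worse) = 2 × Σₖ₌₀¹¹ C(30,k)/2³⁰ = 0.2005.

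**3. Power cost.** For a split n₁:n₂, power comes from the non-central t distribution with non-centrality d/√(1/n₁ + 1/n₂) and n₁ + n₂ − 2 degrees of freedom. For simple randomisation it is averaged over a Binomial(N, 0.5) split.

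| Analysed | Equal arms | Average over simple splits | Cost |
|---|---|---|---|
| 24 | 64.9% (12:12) | 63.0% | 1.9 points |
| 30 | 75.3% (15:15) | 73.8% | 1.5 points |

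A split of 11:19 with everyone analysed gives 72.2%, which is 75.3 − 72.2 = 3.1 points below equal arms.

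If dropout is independent across participants (an assumption), power for a fixed 15:15 list against simple randomisation is:
- 10% dropout: 70.2% against 68.6%.
- 20% dropout: 64.3% against 62.7%.
- 25% dropout: 61.0% against 59.5%.

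**4. After a restricted list.** A list that closes at 30 with equal numbers gives 15:15 with certainty at full enrolment. Dropout can still unbalance the completers under either scheme.

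**5. Weighing.** No arithmetic applies, so the statements are set side by side.
- Only a person without participant interaction knows the arms (5.3).
- Blinded staff weigh each participant's dose (7, 9.2).
- The stock is two products under two brand names (9.1).
- Matching colour hides the dispensed powder from the participant. It does not hide the source container from the weigher.
- The code holder keeps codes electronically and is given no part in handling powder (10.1).
- Marking the tubs 1 and 2 would not mask them, because section 10.1 prints what 1 and 2 mean.

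These statements fit together only if somebody masks the stock before weighing. The supplied text does not describe that step.

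**The case against.** **On allocation.** A reader might infer that the trial is shown to use simple randomisation. The documents do not support that: a list built in advance with fifteen 1s and fifteen 2s in random order would fit the same words. The form's prompt in 10.1 also warns against detail that could compromise the randomisation, which is a fair reason to leave out block sizes. It is not a reason to leave out that the list is restricted. The t-test remains valid with unequal arms, and the loss is under 2 power points on average. All of this stands, and it keeps the allocation part small.

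**On weighing.** The plan does say that the weighers are blinded, and section 9 points to a manual as a place for handling detail. What can be shown is an undescribed mechanism, not a broken blind. Several stronger readings are tempting and are not supported:
- That the weigher necessarily learns each participant's arm. Weight-based dosing ties a participant to a mass and a container. With suitably coded stock the weigher need never know the powder.
- That each daily dose is a separate occasion for unblinding. Section 7 has doses for non-exercise days pre-packaged and provided weekly, and section 9.1 has weekly distribution, so powder may be drawn in batches or from one tub per participant. A count of doses measures no bias.
- That fatigue outcomes will be biased. No section says that weighers coach or assess participants. The same generic staff label appears for weighing, weekly hand-over (9.1) and mixing on exercise days (9.4), but that does not show they are the same people. Equally, no separation between them is stated.

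**Conclusion.** Both parts hold as gaps in specification.

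Allocation: the literal reading secures 15 per arm only 14.4% of the time and costs 1.9 power points at 24 completers or 1.5 at 30, given the plan's effect of 0.25, SD of 0.25 and two-sided t-test. These figures apply only if the list is in fact unrestricted. The case for change is that a better method costs almost nothing, not that the loss is large.

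Weighing: the supplied text claims blinded weighing from two branded products without saying how the blind is kept. This is conditional on the unseen manual and brochure not containing the step. The size of any unblinding bias cannot be computed from the documents, and none is asserted.

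**What to change.** **Section 10.1.** State that the statistician generates and holds a concealed, restricted list giving exactly 15 per arm, for example permuted blocks of varying, undisclosed size totalling 30. The block sizes need not appear in the protocol. Cost: a few lines of code and one sentence. Downside: slight predictability near the end of a block, limited by blinding.

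**Section 9.2.** State that, before weighing, the person who already holds the codes, or another person without participant contact, over-labels the stock or decants it into identical tubs labelled by participant number. The printed 1/2 key should not be used as a label. If someone other than the code holder does this, section 5.3 should name that person among those who know the allocation. If the manual already contains such a step, citing it in 9.2 is enough. Cost: about 30 labellings or decantings, with a log and an error check, because a mislabelled tub would put a participant on the wrong powder.

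Neither change affects sample size, visits or outcomes.

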10.3. Permitted Concomitant Therapy

This section should be consistent with the medication restrictions in the inclusion/exclusion criteria previously listed. Describe how allowed concomitant therapy might affect the outcome (e.g., drug-drug interaction, direct effects on the study endpoints).

There are no medication restrictions except that subjects taking anticoagulant medications must be able to stop temporarily prior to biopsy procedures. Additionally, subjects may not take supplements other than standard multivitamins (calcium, vitamin D, etc.)

10.4. Rescue Medicine

List all medications, treatments, and/or procedures that may be provided during the study for "rescue therapy" and relevant instructions.

N/A, no rescue medicine

11. Study Intervention Discontinuation

11.1. Discontinuation of Study Intervention

Describe the criteria for discontinuing the study intervention (e.g., halting rules), including any monitoring test(s) and associated clinical decision point(s). Include reasons for temporary discontinuation of the study intervention (e.g., type and quantity of adverse events), clearly stating the length of time, if applicable, and describe the data to be collected at the time of study intervention discontinuation and approaches for restarting administration of or re-challenging with study intervention.

Side effects (expected to be minimal) may include gastrointestinal distress (e.g., cramps and gas) and acne, and will be monitored at each exercise session. Any unanticipated or serious side effects will be reported immediately to the study clinical staff, IRB and DSB. Halting the study will be at the discretion of the study clinical staff and/or DMSB. There is no risk of stopping the study supplements early or abruptly.

11.2. Continued Follow-up Discontinuation of Study Intervention

Describe efforts that will be made to continue follow-up of participants who discontinue the study intervention, but remain in the study for follow-up, especially for safety and efficacy study endpoints (if applicable). Reasonable efforts must be made to undertake protocol-specified safety follow-up procedures to capture adverse events (AE), serious adverse events (SAE), and unanticipated problems involving risks to subjects or others (UPIRSOs).

Participants who withdraw from the study will be contacted by study staff via both telephone and mail to encourage post-intervention testing.

12. Statistical Considerations

12.1. Statistical Hypotheses

State the formal and testable null and alternative hypotheses for primary and key secondary endpoints, specifying the type of comparison (e.g., superiority, equivalence or non-inferiority, dose response) and time period for which each endpoint will be analyzed.

Our central hypothesis is that eight weeks of BCAA added to exercise will increase expression of KATs, shifting kynureneine metabolism towards enhanced synthesis of kynurenic acid, thereby reducing fatigue.

12.2. Sample Size Determination

Include number of participants to recruit, screen, and enroll to have adequate power to test the key hypotheses for the study. Provide all information needed to validate your calculations and judge the feasibility of enrolling and following the necessary number of participants.

An important goal of statistical analyses is to determine effect sizes to make certain that future studies evolving from the current work are adequately powered. While data do not exist to provide more precise effect sizes for the current experiment, based upon previous studies (Millischer et al., 2017), a $0.64 \pm 0.19 \mu\text{mol/L}$ decrease in kynureneine concentration was observed following exercise training. The anticipated additive effect of BCAA supplementation is $0.25 \mu\text{mol/L}$. Assuming a SD of $0.25 \mu\text{mol/L}$, 12 subjects per group are necessary to achieve at least 80% power with a 5% level of significance. To allow for a 20% dropout, we will recruit a total of 30 subjects with the intent of having 24 complete.

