12.4. Statistical Analyses

Include analysis of primary efficacy endpoints, secondary endpoints, safety analyses, and any planned interim analyses

In collaboration with RC3 (Trial Design and Integrative Informatics Core), two separate independent sample t-tests will be used for each outcome measure: one to compare change before and after acute exercise (during the 400 m walk) between the two groups and one to compare change before and after chronic (8-week) exercise training between the two groups. This will determine the significance of our primary outcomes (fatigue and tryptophan metabolism) change over time. All statistical tests will be 2-sided and unadjusted for multiple comparisons. We are eschewing the mixed model analysis of variance (ANOVA) to account for the time effect. The repeated measures ANOVA would be testing more effects than we are exploring here, and the study is not powered for this advanced analysis.

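### On the plan's own inputs, 12 completers per group give about 65% power, not the stated 80% or more

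*Combined protocol and SAP*

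**What the plan says.** Section 12.2 (Sample Size Determination) starts from an earlier study in which kynurenine fell by 0.64 ± 0.19 µmol/L after exercise training. It then sets the between-group effect: "The anticipated additive effect of BCAA supplementation is" 0.25 µmol/L. It assumes an SD of 0.25 µmol/L and concludes that "12 subjects per group are necessary to achieve at least 80% power with a 5% level of significance". Allowing for 20% dropout, it arrives at 30 recruits for 24 completers. Section 5.1 carries the same targets: "30 screened and enrolled (n=24 completers").

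Section 12.4 (Statistical Analyses) names the test: "two separate independent sample t-tests will be used for each outcome measure", one for change across the acute walk test and one for change across the eight weeks, each comparing the two groups. It adds: "All statistical tests will be 2-sided and unadjusted for multiple comparisons".

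**The concern.** Sections 12.2 and 12.4 together supply everything needed to check the power: difference, SD, group size, significance level, sidedness and test. A difference of one SD with 12 per group looks too small for 80% power in a two-sided two-sample test.

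This is the plan's only quantitative power statement, and both enrolment targets derive from it. If it is wrong, readers will give a null kynurenine result the weight of an 80%-powered comparison that the trial did not have.

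**Working it through.** **Inputs**

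- Difference in change between groups: δ = 0.25 µmol/L (12.2)
- SD: σ = 0.25 µmol/L (12.2), taken as the SD of the change, because change is what the planned test analyses
- n = 12 completers per group (12.2), allocation 1:1 (5.3)
- α = 0.05 (12.2), two-sided (12.4)
- Test: independent-sample t-test (12.4)

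Standardised difference: d = 0.25 / 0.25 = 1.0.

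**Attempt to reproduce the stated figure**

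Non-centrality: d × √(n/2) = 1.0 × √6 = 2.449, with 2 × 12 − 2 = 22 degrees of freedom.

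Two-sided power from the non-central t distribution is **64.9%**. A simulation of 400,000 trials gives 64.8%. The stated 80% or more is not reproduced; the gap is about 15 percentage points.

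**Group size needed for 80%**

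| n per group | Power, two-sided 5% t-test |
|---|---|
| 12 | 64.9% |
| 15 | 75.3% |
| 16 | 78.1% |
| 17 | 80.7% |

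So 17 completers per group are needed. The row for 15 is the case in which all 30 participants complete.

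**Other ways the 12 might have arisen**

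- Normal approximation, two-sided: Φ(2.449 − 1.960) = Φ(0.489) = 68.8%. Required n = 2 × (1.960 + 0.842)² / 1.0² = 15.7, so 16 per group.
- One-sided 5%, t-test: 76.7%, needing 14 per group.
- One-sided 5%, normal approximation: Φ(2.449 − 1.645) = Φ(0.804) = 78.9%, needing 13 per group.
- SD of 0.19 (the ± figure from the earlier study, if it is an SD), two-sided t-test: 86.9%, needing 11 per group. Section 12.2 explicitly assumes 0.25 instead.
- One-sample or paired t-test with n = 12: 88.3%. This is not the planned test.

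**If 0.25 is a single-visit SD**

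The SD of the change is then 0.25 × √(2(1 − r)), where r is the pre-post correlation. The plan gives no r, so the values below are assumptions.

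| r | SD of change | Power, 12 per group |
|---|---|---|
| 0 | 0.354 | 38% |
| 0.5 | 0.250 | 65% |
| 0.65 | 0.209 | 80% |
| 0.7 | 0.194 | 86% |

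**What 12 per group can detect with 80% power**

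The standardised difference must be 1.197. That means a difference of 1.197 × 0.25 = 0.299 µmol/L at the assumed SD, or an SD of 0.25 / 1.197 = 0.209 µmol/L at the assumed difference.

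**Dropout step**

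24 / 0.8 = 30. This step is correct; the error lies in the 12.

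**The case against.** The strongest counter-argument is that section 12.2 does not say which SD it means. If 0.25 is the SD of a single measurement and pre and post values correlate at 0.65 or more, 12 per group does reach 80%. That reading is possible, and the 65% figure depends on rejecting it. But it needs a correlation that appears nowhere in the plan. It also fits the text poorly: the SD follows directly on a change and an added effect on that change, and the planned test analyses change.

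A second argument is that section 12.2 states no sidedness, and a one-sided normal approximation comes close, at 78.9%. That may explain where the 12 came from. It still falls short of 80%, and section 12.4 makes every test two-sided.

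A third is that the consequence is modest. Section 12.2 names estimation of effect sizes for later studies as an important goal and admits that data for a more precise planning value are lacking. The calculation also covers kynurenine only and says nothing about fatigue. These points stand, and they limit how much weight the power figure should carry. They do not make it correct, and section 12.4 still uses the t-tests to judge the significance of the primary outcomes.

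**Conclusion.** The concern holds. With a difference of 0.25 µmol/L, a change-score SD of 0.25 µmol/L and the two-sided 5% independent-sample t-test that the plan specifies, 12 per group give 64.9% power. The type II error is about 35%, against the 20% or less implied by the text. For 80% power, 17 completers per group are needed, five more than stated.

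The result rests on the SD being that of the change. Under the single-visit reading, power runs from 38% (r = 0) to 86% (r = 0.7), so the sentence would still be unsupported without a stated correlation.

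**What to change.** Replace the power sentence in section 12.2 with wording such as: *Twelve completers per group give about 65% power (two-sided 5% independent-sample t-test) to detect a between-group difference in change of 0.25 µmol/L, assuming an SD of the change of 0.25 µmol/L; 80% power is reached for a difference of about 0.30 µmol/L.* If the SD is in fact that of a single measurement, say so and give the assumed pre-post correlation with its source.

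This costs one sentence and a less favourable stated power. It needs no extra participants and leaves the targets of 24 completers and 30 recruits in place.

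If the sponsor would rather keep the 80% claim for 0.25 µmol/L, the price is 34 completers. At 20% dropout that is 34 / 0.8 = 42.5, so 43 recruits, or 44 with equal arms of 22, against the 30 planned.
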